7.7.3.2 Follow-up visits

When a subject discontinues study treatment, for whatever reason (PD/iCPD, unacceptable toxicity, or withdrawal of consent), the subject will move into the follow-up phase. The patient will be assessed every 3 months (± 7 days) the first year after discontinuation to monitor disease status. Every effort will be made to collect information regarding disease status until the start of a new anti-neoplastic therapy, disease progression, death, or end of the study. Information regarding post-study anti-neoplastic treatment will be collected if new treatment is initiated.

7.7.3.3 Survival follow-up

Once a subject discontinues study treatment or starts a new anti-cancer therapy, the subject moves into the survival follow-up phase. We will monitor survival status every 6–12 months (by phone call, subject visit, contact with patient's general practitioner) until the end of the study. The survival status and, if applicable, the cause of death will be recorded.

7.7.4 Withdrawal or discontinuation

When a subject discontinues or withdraws prior to trial completion, all applicable activities scheduled for the final trial visit will be performed at the time of discontinuation. Any AE which are present at the time of discontinuation will be followed in accordance with the safety requirements outlined in [Chapter 8](#).

Subjects may withdraw consent at any time for any reason or be dropped from the trial at the discretion of Clinical Investigator should any untoward effect occur. In addition, a subject may be withdrawn by Clinical Investigator or Sponsor if enrolment into the trial is inappropriate, the trial plan is violated, or for administrative and/or other safety reasons. A subject must be discontinued from the trial for any of the following reasons:

- AE/SAE as specifically described.
- The subject withdraws consent.
- Confirmed disease progression; *c.f.*, [Paragraph 7.6](#).
- Any clinical AE, laboratory abnormality, or intercurrent illness which, in the opinion of Clinical Investigator, indicates that continued participation in the study is not in the best interest of the subject.
- Intercurrent illness that prevents further administration of treatment.
- Clinical Investigator's decision to withdraw the subject.
- The subject has a confirmed positive pregnancy test.
- Non-compliance with trial treatment or procedure requirements.
- The subject is lost to follow-up.
- Administrative reasons.

After the end of treatment, each subject will be followed for 30 days for AE monitoring. Subjects who discontinue for reasons other than PD/iCPD will have post-treatment follow-up for disease status until disease progression, starting a non-study cancer treatment, withdrawing consent, or becoming lost to follow-up. After documented disease progression, information on survival will be obtained until death, withdrawal of consent, or the end of the study, whichever occurs first.

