5.5 Duration of therapy

The **control arm** will consist of intermittent treatment with the Nordic FLOX regimen in terms of 8 cycles (16 weeks) before a break until disease progression, when therapy is reintroduced and administered for another 8 cycles before a new break. This go-and-stop schedule, which is chosen because continuous FLOX treatment commonly causes unacceptable toxicity in the palliative setting, will be continued until progressive disease on ongoing therapy (defining PFS in terms of failure of treatment strategy), unacceptable toxicity, withdrawal of consent, or death, whichever occurs first.

The estimated median PFS in the control arm is 9 months (*i.e.*, 39 weeks), as detailed in [Chapter 10](#). During this period, it is assumed that the ‘average’ patient will receive 1 full go-and-stop treatment sequence, consisting of 16 weeks of active therapy followed by 8 weeks of break until disease progression, before the second treatment period results in progressive disease after 16 weeks on ongoing therapy; hence, a PFS of 40 weeks. During the entire treatment, this patient will receive 2 sequences of active therapy, each containing 8 FLOX cycles.

The **experimental arm** will consist of repeat 2 cycles of the Nordic FLOX regimen followed by 2 cycles of nivolumab for a total of 8 individual cycles (16 weeks) before a break until disease progression, when therapy is reintroduced and administered for another total of 8 individual cycles before a new break. This go-and-stop schedule will be continued until progressive disease on ongoing therapy (defining PFS in terms of failure of treatment strategy), unacceptable toxicity, withdrawal of consent, or death, whichever occurs first.

[figure not shown]

Figure 4 – the experimental treatment arm.

The estimated median PFS in the experimental arm is 18 months (*i.e.*, 78 weeks), as detailed in [Chapter 10](#). During this period, it is assumed that the ‘average’ patient will receive 3 full go-and-stop treatment sequences, each consisting of 16 weeks of active therapy followed by 8 weeks of break until disease progression, before the fourth treatment period results in progressive disease after 8 weeks on ongoing therapy; hence, a PFS of 80 weeks. During the entire treatment, this patient will receive 4 sequences of active therapy, each containing 4 cycles each of FLOX and nivolumab.

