7.6.6. Date of progression

This is defined as the first day when RECIST (v1.1) PD is observed in the control arm and after iRECIST iCPD is observed in the experimental arm.

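### Protocol 7.7.4 makes confirmed progression a mandatory exit from the trial without the on-therapy condition on which the go-and-stop schedule in 5.5 depends

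*Protocol*

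**What the plan says.** **The exit rule.** Protocol 7.7.4 states: "A subject must be discontinued from the trial for any of the following reasons". The third bullet is "Confirmed disease progression", followed by a reference to 7.6. The last sentence of 5.7.2.4 likewise stops study treatment permanently once progression is confirmed.

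**The treatment rule.** Section 5.5 describes a go-and-stop schedule. In the control arm, eight FLOX cycles are given "before a break until disease progression, when therapy is reintroduced and administered for another 8 cycles before a new break". In the experimental arm, the eight alternating cycles are given "before a break until disease progression, when therapy is reintroduced and administered for another total of 8 individual cycles before a new break". In both arms the schedule is "continued until progressive disease on ongoing therapy (defining PFS in terms of failure of treatment strategy"), or until toxicity, withdrawal of consent or death. Footnote 1 of the flow chart (section 6) states the same rule, and footnote 2 says that the break runs until progression.

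**The exception in 5.5.** Experimental-arm patients who complete 24 months of active sequential therapy and then progress, on or off FLOX alone, may restart FLOX and nivolumab at the investigator's discretion.

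**Follow-up after exit.** Section 7.7.4 says "Subjects who discontinue for reasons other than PD/iCPD will have post-treatment follow-up for disease status until disease progression" and "After documented disease progression, information on survival will be obtained until death, withdrawal of consent, or the end of the study".

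**The concern.** Progression in a break is an expected step in this design. It is the signal to treat again. The exit rule does not distinguish it from progression on therapy, which is the failure that 5.5 uses to define PFS. If a patient's progression is confirmed during a break, a site cannot obey both sections: 7.7.4 requires exit and 5.5 requires re-treatment.

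If a site followed 7.7.4, the repeat sequences would not be given on trial. Failure of the treatment strategy might then never be observed for that patient. The 24-month exception would also be overridden, because the bullet makes no allowance for it.

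**Working it through.** **1. The rules side by side (Protocol)**

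| Place | Trigger | On-therapy condition | Consequence |
|---|---|---|---|
| 7.7.4, third bullet | confirmed progression, see 7.6 | none | must leave the trial |
| 5.7.2.4, last sentence | progression confirmed | none | study treatment stops for good |
| 5.5, both arms | progression in a break | not applicable | therapy restarts |
| 5.5, both arms | progression on ongoing therapy | yes | failure of strategy |
| Flow chart, footnote 1 | progression in a break, then on therapy | yes, for stopping | repeat the sequence, then stop |

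**2. Does the pointer to 7.6 supply the condition?** No. Section 7.6.6 dates progression at the "first day when RECIST (v1.1) PD is observed in the control arm and after iRECIST iCPD is observed in the experimental arm", whether or not the patient is on a break. Section 7.6.1 counts the first recorded progression. It mentions breaks only to say that the Study Radiologist is told of them.

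**3. Does the word confirmed supply it?** Not in the control arm: Appendix 2 says that RECIST 1.1 progression needs no confirmation unless equivocal. In the experimental arm, 7.6.4 requires the next assessment, 4 to 8 weeks after unconfirmed progression (iUPD), before confirmed progression (iCPD) is assigned. That delays the trigger but does not tie it to therapy.

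**4. Size on the average course in 5.5**

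The inputs from 5.5 are 16 weeks of active therapy per sequence and 8 weeks of break until progression. The control patient fails after 16 weeks of the second sequence, and the experimental patient after 8 weeks of the fourth.

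The protocol's own figures reproduce:
- Control: 16 + 8 + 16 = 40 weeks.
- Experimental: 3 × (16 + 8) + 8 = 80 weeks.

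Under a literal reading of 7.7.4, with first progression in the first break at 16 + 8 = 24 weeks:
- Control: exit at week 24, which is 40 − 24 = 16 weeks early, after 8 of 2 × 8 = 16 FLOX cycles.
- Experimental, with iUPD at week 24: iCPD at 24 + 4 = 28 to 24 + 8 = 32 weeks. Exit is 80 − 28 = 52 to 80 − 32 = 48 weeks early.

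The experimental figure assumes that the site treats iCPD as confirming the break progression. If therapy had already restarted and the tumor grew further on it, exit would be correct under 5.5 as well.

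**5. Imaging after such an exit.** Section 7.6.5 keeps 8-weekly evaluation after discontinuation only for patients without progression. The disease-status follow-up in 7.7.4 is for those who stopped for other reasons. Section 7.7.3.2 schedules 3-monthly visits in the first year, also after progression, but the flow chart marks no CT for them. No later scan is therefore mandated.

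**6. Number of patients affected.** This needs the rate of confirmed progression in breaks. The documents give none, so no number or bound is offered.

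**The case against.** The strongest reply is that the protocol already settles the matter. Section 5.5 states the re-treatment rule separately for each arm, the flow chart repeats it, and the synopsis and section 3 give treatment duration as lasting until the strategy fails. A general withdrawal list would hardly override all of that. This stands, and it is why the point is minor. It does not remove the conflict, because the withdrawal list is worded as mandatory.

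A second reply is that confirmed in 7.7.4 echoes 5.7.2.4, which concerns patients continuing treatment after suspected progression, so an on-treatment setting is implied. That is a coherent reading, but it does not supply the missing words, and confirmation filters nothing in the control arm unless progression is equivocal.

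A reader might also infer more than the documents support:

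- *Experimental exit at week 24, 56 weeks early (80 − 24).* Progression first seen at week 24 is only iUPD under 7.6.4, and confirmation takes a further 4 to 8 weeks.
- *A fraction of experimental cycles lost, such as 8 of 28.* By week 80, 3 × 8 + 4 = 28 cycles are due, but 5.5 credits the average patient with four full sequences, or 4 × 8 = 32. Therapy may also have restarted before confirmation. No fraction is claimed.
- *A second, independent defect in imaging.* A patient removed early receives no further study therapy, so there is no on-therapy failure left to detect. The lost observation follows from the exit.
- *A failure of the design or complete loss of data.* Section 5.5 makes the intent plain, and survival follow-up continues after exit.

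**Conclusion.** The rule is wrong as written, and the error is minor. The progression bullet in 7.7.4 and the last sentence of 5.7.2.4 lack the on-therapy condition found in 5.5 and flow chart footnote 1. Taken literally, the first ends trial participation, and the second ends study treatment, at an event for which 5.5 prescribes re-treatment. The likely harm is misapplication at individual sites.

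The illustration is exit 16 weeks early for a control patient and about 48 to 52 weeks early for an experimental patient. It rests on the average course in 5.5, a literal reading of 7.7.4, and first progression at week 24 (iUPD in the experimental arm). It describes one patient's course and does not estimate an effect on the trial.

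Whether progression in a break counts as a PFS event under 7.6.1, 7.6.6 and 10.4.1 is a separate question, which correcting 7.7.4 does not settle.

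**What to change.** Replace the 7.7.4 bullet with:

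> Confirmed disease progression (c.f. 7.6) on ongoing study therapy, i.e., failure of treatment strategy (c.f. 5.5), except where 5.5 permits reinstitution after 24 months of active therapy. Progression during a planned break leads to reintroduction of therapy and is not by itself a reason for discontinuation; further progression after therapy is reintroduced counts as progression on ongoing therapy. 8-weekly imaging continues until failure of treatment strategy.

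The clause on further progression matters. Without it, a patient whose break progression continues on reintroduced therapy could be kept on study treatment.

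Three consistency edits go with it:
- Add *on ongoing therapy, subject to 5.5* to the last sentence of 5.7.2.4.
- In 7.6.5, word the post-discontinuation imaging rule in terms of failure of treatment strategy instead of progression.
- In 7.7.4, do the same for the sentence that moves patients to survival follow-up after documented progression.

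Section 5.5 and footnote 1 need no change. The cost is one bullet and three short wording edits, handled as an amendment under 11.4. No procedure is added, because 7.6.5 already requires 8-weekly evaluation in both arms and during planned breaks.

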7.8 End of study

The end of study is defined as “last patient last visit”, in accordance with European Commission guidelines. However, as mentioned in [Paragraph 5.5](#), accumulating evidence from a number of clinical trials in different tumor types with nivolumab indicates that patients may obtain durable responses, even if they discontinue nivolumab for toxicity. Such observations are acknowledged as general features of ICB [Emens *et al.*, 2017] and may call for a redefinition of the end-of-study term during the study conduct.

7.9 Study termination

Early trial termination may be the result of one of the following criteria:

- Quality or quantity of data recording is inaccurate or incomplete.
- Poor adherence to protocol and regulatory requirements.
- Incidence or severity of adverse drug reaction in this or other studies indicates a potential health hazard to subjects.
- Plans to modify or discontinue the development of the study drug.

In the event of BMS decision to no longer supply study drug, ample notification will be provided so that appropriate adjustments to subject treatment can be made.

The whole trial may be discontinued at the discretion of Principal Investigator or Sponsor in the event of any of the following:

- Occurrence of AE/SAE unknown to date in respect of their nature, severity, and duration.
- Medical or ethical reasons affecting the continued performance of the trial.
- Difficulties in the recruitment of patients.
- Cancellation of drug development.

Sponsor and Principal Investigator will inform all investigators and the relevant Competent Authorities and Ethics Committees of the termination of the trial along with the reasons for such action. If the study is terminated early on grounds of safety, the Competent Authorities and Ethics Committees will be informed within 15 days.

7.10 Ancillary study procedures

The below listed procedures do not represent a mandatory list of what are to be performed, but instead provide an overview of the current plans. The priority of analyses and assays will be subject to review during and after finalization of the trial. Additional investigations may be performed, reflecting ongoing developments in the field. Some assays will be performed only for selected patients because of costs and work load.

For the precise timing of the various procedures described below, please refer to the Study Flow Chart – Chapter 6.

7.10.1 Repeat quality-of-life recording

Formal QoL recording will undertaken at study enrolment, completion of the active therapy of the first treatment sequence (after 16 weeks), and disease progression, using the consensus modules EORTC QLQ-C30, EORTC QLQ-CIPN20, and EQ-5D-5L (<http://groups.eortc.be/qol/>, <http://www.euroqol.org/>). Please refer to the information in Appendices 7–9.

Participation in the QoL sub-study is mandatory for study centers.

7.10.3 Repeat collection of PBMC

Currently, no robust biomarker of cytotoxic T cell activity exists for clinical use, but PTEN phosphatase activity is high in T lymphocytes silenced by PD-1 binding to PD-L1 [Riley, 2009; Patsoukis *et al.*, 2013]. Building on our long-standing collaboration with the Dutch biotechnology company PamGene International B.V. (www.pamgene.com), we will apply their recently developed phosphatase array [Hovestad-Bijl *et al.*, 2016] on PBMC samples [Noé *et al.*, 2016], as readily accessible surrogate tissue for the monitoring of cytotoxic T cell activity, at the proteomic facility at Department of Clinical Molecular Biology, Akershus University Hospital [[name] *et al.*, 2015].

Moreover, together with Department of Cellular Therapy / Immunomonitoring Laboratory, Oslo University Hospital, *ex vivo* cytokine analysis, applying the ELISPOT assay, will be done on PBMC or specific subsets of CD4-positive and CD8-positive T cells.

One tube of 10 mL peripheral blood will be drawn for this purpose immediately before start of treatment and after every completed 2 therapy cycles (immediately before start of the next cycle or at treatment interruption) until disease progression, unacceptable toxicity, withdrawal of consent, death by any reason, or end-of-follow-up, whichever occurs first, and every 8 weeks during planned treatment breaks. PBMC will be isolated by density-gradient centrifugation in Ficoll, stored at –80°C at the local study center, and dispatched to the study biobank at Akershus University Hospital upon request. Please refer to the specified SOP document (in Investigator Site File).

Participation in the above-mentioned circulating biomarker sub-studies is optional for study centers.

7.10.4 Repeat functional MR imaging

Experimental arm patients will undergo repeat MR recordings of abdominal metastases at time points corresponding to each change of therapy (from FLOX to nivolumab and reverse) during the first two months of the sequential regimen (*i.e.*, three recordings in total), using a discrete number of functional MR sequences with readouts reflecting TME biology. Specifically, we will apply our recently developed multi-echo contrast-enhanced sequence, which can predict metastatic progression with high diagnostic accuracy [Grøvik *et al.*, 2016]. Importantly, the MR procedure must be done before a metastatic lesion is sampled by biopsy. Control arm patients may be exempt from MR imaging at the discretion of Clinical Investigator. Please refer to the specified SOP document (in Investigator Site File).

Participation in the functional MR imaging biomarker sub-study is optional for study centers.

7.10.5 Repeat collection of metastatic tissue

Experimental arm patients will undergo repeat sampling of core biopsies from liver/peritoneal metastases at time points corresponding to each change of therapy (from FLOX to nivolumab and reverse) during the first two months of the sequential regimen (*i.e.*, three sampling procedures in total; one or both of the resampling procedures, *i.e.*, others than that at baseline, are excused if the total number of three procedures is not feasible). Control arm patients will undergo biopsy sampling at baseline and may also be exempt from repeat sampling at the discretion of Clinical Investigator. For an individual patient, repeat sampling will preferentially be from the same lesion every time. The sampling procedure will be ultrasound-guided. Ideally, to ensure that the material from the sampling locus is representative, a regular smear from a fine-needle aspirate will be assessed by a pathologist at site. Next, 1–3 core biopsies will be taken and tumor cell content estimated by tissue imprint prior to freezing in liquid nitrogen [[name] *et al.*, 2017]. The samples will be dispatched to the study biobank at Akershus University Hospital upon request. Please refer to the specified SOP document (in Investigator Site File).

The 1–3 biopsy samples will be utilized in the following priority: 1) histology/immune histochemistry, 2) RNA applications, and 3) DNA applications. Specifically, the total number of T cells (CD3-positive) will be determined, with identification of T cell subpopulations by their expression of specific proteins (CD8-positive cytotoxic and FoxP3-positive regulatory T cells), as recently shown in a pilot study (Dagenborg *et al.*, manuscript in preparation). Also, CRC liver metastasis samples were recently analyzed by gene expression microarrays and indicated immune activity profiles in patients who had received neoadjuvant FLOX [Østrup *et al.*, 2017]. Comprehensive gene mutation analysis will be done [[name] *et al.*, 2017]. Of note, a number of RNA-based methods will be applied to specifically investigate novel mechanisms of anti-tumor immunity. Also, tumor PD-L1 expression, consensus molecular subtype, and mutation burden may be determined.

Participation in the histologic and molecular investigational sub-studies is mandatory (baseline biopsy sampling; follow-up biopsy sampling is optional) for study centers.

8 SAFETY MONITORING AND REPORTING

The investigators are responsible for the detection and documentation of events meeting the criteria and definition of AE or SAE. Each patient will be instructed to contact Clinical Investigator immediately should they manifest any signs or symptoms they perceive as serious.

8.1 Definitions

An AE is defined as any new untoward medical occurrence or worsening of a preexisting medical condition in a subject administered a study drug and which does not necessarily have a causal relationship with this treatment. An AE can therefore be any unfavorable and unintended sign (including an abnormal laboratory finding), symptom, or disease temporally associated with the use of a medicinal (investigational) product, whether or not cautiously related to the medicinal (investigational) product.

The causal relationship to a study drug is determined by a physician and can be one of the following:

- Related: There is a reasonable causal relationship between study drug administration and the AE.
- Not related: There is not a reasonable causal relationship between study drug administration and the AE.

The term “reasonable causal relationship” means there is evidence to suggest a causal relationship. AE can be spontaneously reported or elicited during open-ended questioning, examination, or evaluation of a subject.

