5.7.2.3 Treatment discontinuation criteria for IMP

For nivolumab, treatment will be permanently discontinued for the following reasons (in CTCAE grading):

- Any grade 4 drug-related AE.
- Any grade 2 drug-related uveitis, eye pain, or blurred vision that does not respond to topical therapy and does not improve to grade 1 severity within the re-treatment period or requires systemic treatment.
- Any grade 3 non-skin, drug-related AE lasting >7 days, with the following exceptions for laboratory abnormalities, drug-related uveitis, pneumonitis, bronchospasm, hypersensitivity reactions, infusion reactions, and endocrinopathies:
 - Grade 3 drug-related uveitis, pneumonitis, bronchospasm, hypersensitivity reaction, or infusion reaction of any duration (requires discontinuation).
 - Grade 3 drug-related endocrinopathies that are adequately controlled with only physiologic hormone replacement (do not require discontinuation).
 - Grade 3 drug-related laboratory abnormalities (do not require treatment discontinuation) except grade 3 drug-related thrombocytopenia >7 days or associated with bleeding (requires discontinuation).
- Any drug-related liver function test abnormality that meets the following criteria (requires discontinuation):
 - AST or ALT >5xULN.
 - Total bilirubin >3xULN.
- Any grade 4 drug-related AE or laboratory abnormality, except for one of the following events (does not require discontinuation):
 - Grade 4 neutropenia ≤7 days.
 - Grade 4 lymphopenia or leukopenia.
 - Isolated grade 4 amylase or lipase abnormalities that are not associated with symptoms or clinical manifestations of pancreatitis. Study Conduct Group (*c.f.*, [Paragraph 11.3](#)) should be consulted for grade 4 amylase or lipase abnormalities.
 - Isolated grade 4 electrolyte imbalances/abnormalities that are not associated with clinical sequelae and are corrected with supplementation/appropriate management within 72 hours of their onset.
 - Grade 4 drug-related endocrinopathy adverse events, such as adrenal insufficiency, ACTH deficiency, hyper- or hypothyroidism, or glucose intolerance, which resolve or are adequately controlled with physiologic hormone replacement (corticosteroids, thyroid hormones) or glucose-controlling agents, respectively, may not require discontinuation after discussion with and approval from Study Conduct Group.

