8.9 AE (adverse events) recording

If the patient has experienced an AE, Clinical Investigator will record the following information in the CRF:

- The nature of the AE will be described in precise standard medical terminology (*i.e.*, not necessarily the exact words used by the patient).
- The duration of the event will be described in terms of event onset date and event ended date.
- The intensity of the AE will be defined according to CTCAE v4.0.
- The causal relationship of the event to the IMP will be assessed as one of the following:

Unrelated: There is no temporal relationship to IMP administration (too early or late, or IMP not administered), or there is a reasonable causal relationship between non-investigational product, concurrent disease, or circumstance and the AE.

Unlikely: There is a temporal relationship to IMP administration, but there is not a reasonable causal relationship between the IMP and AE.

Possible: There is reasonable causal relationship between the IMP and AE. Dechallenge information is lacking or unclear.

Probable: There is a reasonable causal relationship between the IMP and AE. The event responds to dechallenge. Rechallenge is not required.

Definite: There is a reasonable causal relationship between the IMP and AE.

- Action taken.
- The outcome of the AE – whether the event is resolved or still ongoing.

It is important to distinguish between serious and severe AE. Severity is a measure of intensity whereas seriousness is defined by the criteria in Paragraph 8.1.2. An AE of severe intensity needs not necessarily be considered serious. For example, nausea that persists for several hours may be considered severe nausea, but is not an SAE. On the other hand, a stroke that results in only a limited degree of disability may be considered a mild stroke, but would be an SAE.

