#### 5.2. Analysis methods

*Main statistical analyses.* The main statistical analysis is planned after the last patient has fulfilled the pre-defined follow-up period. PFS will be calculated from the day of randomization to first recorded disease progression according to RECIST v1.1 or when applicable iRECIST, or death. Patients who have not had disease progression at the time of final analysis will be censored at the date last known to be alive and progression-free. The analyses will compare the treatment groups in total as well as groups stratified by primary tumor sidedness and (K)RAS/BRAF mutation status.

*Interim analyses.* Interim analyses will apply to data on safety, tolerability, possible detrimental effects, and curative outcomes, and will be based on purely clinical judgment by the External Data and Safety Monitoring Committee. These types of data will be reported as the number of events.

*Descriptive statistics.* Demographic and clinical characteristics will be presented as means and standard deviations, medians with minimum and maximum values, or frequencies and percentages, as appropriate. Further statistical analyses will be separated to primary analyses, including only comparison of primary end point between two treatment arms, and secondary analyses, including stratified analyses on primary and secondary end points as well as number of analyses on secondary end points.

*Primary analysis.* Median PFS time will be compared between study arms by drawing Kaplan-Meier survival curves and performing log-rank test. HR with the corresponding 95% CI and p-values will be estimated by Cox proportional hazards model.

*Secondary analyses.* Distribution of PFS times stratified by the primary tumor sidedness and (K)RAS/BRAF mutation status will be illustrated graphically by Kaplan-Meier curves and compared by log-rank test. To assess the hazard rates for disease progression within each strata, Cox proportional hazards model will be estimated and, if appropriate, adjusted for relevant covariates. The results will be presented as HR with the corresponding 95% CI and p-values.

Safety. The number of serious adverse events (SAE) will be summarized and presented by trial arm. In addition, information will be given on the number of SAE per participant, together with details on the causality, expectedness, and outcome of each SAE experienced. Summaries of suspected unexpected serious adverse reaction (SUSAR) events will also be presented by trial arm.

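### Protocol 8.1 and 8.9 classify an adverse event with both a plausible drug cause and a plausible other cause differently, and no text says which section governs

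*Protocol*

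**What the plan says.** Protocol 8.1 gives two categories. The positive one is "Related: There is a reasonable causal relationship between study drug administration and the AE" and the negative one is "Not related: There is not a reasonable causal relationship between study drug administration and the AE". The threshold is low: a reasonable causal relationship "means there is evidence to suggest a causal relationship". Neither category mentions alternative causes.

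Protocol 8.9 lists what the investigator enters in the CRF. It introduces five categories (Unrelated, Unlikely, Possible, Probable, Definite) with "The causal relationship of the event to the IMP will be assessed as one of the following". 'Unrelated' has two limbs. The first is the absence of a temporal relationship to IMP administration. The second is introduced by a plain alternative: "or there is a reasonable causal relationship between non-investigational product, concurrent disease, or circumstance and the AE". 'Unlikely' needs a temporal but no reasonable causal relationship to the IMP. 'Possible', 'Probable' and 'Definite' all need a reasonable causal relationship to the IMP.

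Relatedness is then used in several places, none of which names a scale:

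- Protocol 8.2 requires an SAE after the collection window to be reported if it is believed related to an IMP or a protocol procedure.
- Protocol 8.10.1 has the sponsor evaluate the causality of reported SAE.
- SAP 5.2 presents SAE by arm "together with details on the causality, expectedness, and outcome of each SAE experienced", and SAP 5.5 names causality as one of the dimensions of safety reporting.
- The nivolumab delay, resumption and discontinuation rules in Protocol 5.7.2.1 to 5.7.2.3 use the term, for example "Any grade 4 drug-related AE".

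**The concern.** In metastatic colorectal cancer the disease itself is often a candidate explanation for an adverse event. Protocol 4.3 requires an intra-abdominal metastatic lesion and, when the liver is involved, admits patients with AST/ALT up to 5xULN. Protocol 5.7.2.3 then has a nivolumab discontinuation criterion for a drug-related AST or ALT above 5xULN. In such a patient both explanations may be reasonable, and the attribution rule decides how the event is classified.

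If two sections allow opposite entries for the same facts, recorded causality depends partly on which section the investigator follows. The trial is open-label, so that choice is made with the arm known. At stake are the reliability of the causality information in a trial that lists safety and tolerability among its superiority questions, and the reporting of late serious events, where the investigator's belief about relatedness is itself the trigger.

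**Working it through.** No arithmetic applies: the plan gives no figure on this point, and the question is whether two sets of definitions agree. I coded each definition by three facts about an event: T, a temporal relationship to IMP administration; D, a reasonable causal relationship to the drug; A, a reasonable causal relationship to something else (disease, another product, circumstance).

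- 8.1: Related = D. Not related = not D.
- 8.9: Unrelated = (not T) or A. Unlikely = T and not D. Possible, Probable and Definite each require D, and differ mainly in the dechallenge information.

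| T | D | A | 8.1 | 8.9 | Agreement |
|---|---|---|---|---|---|
| yes | yes | no | Related | Possible, Probable or Definite | yes |
| yes | no | no | Not related | Unlikely | yes |
| yes | no | yes | Not related | Unrelated (also meets Unlikely) | yes, in direction |
| yes | yes | yes | Related | Unrelated, and also Possible or higher | **no** |
| no | any | any | depends on D | Unrelated | yes, unless D is judged present despite the timing |

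The conflict is in the fourth row. Because the second limb of Unrelated needs only A, a dual-cause event satisfies it while also satisfying Possible (or Probable, if it responds to dechallenge). The CRF scale asks for one category, so two opposite entries comply with the text, and one of them contradicts 8.1. I found no sentence in either document that gives one section precedence or maps five levels to two. The last row is only a boundary case.

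I then followed where the recorded category matters.

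- **SAE inside the collection window.** Protocol 8.2 sends every SAE to the sponsor within 24 hours regardless of attribution, and 8.10.1 has the sponsor evaluate causality. The investigator's entry does not stop that evaluation, though the sponsor's scale is not stated.
- **SAE after the window.** Under 8.2 the duty to report depends on the investigator believing the event related. An event judged unrelated need not reach the sponsor, so there is no second look.
- **Non-serious AE.** Sponsor causality evaluation is described for SAE only.
- **SAP output.** SAE counts and CTCAE grades by arm in SAP 5.2 carry no stated relatedness filter and do not change. The causality details in 5.2 and the causality dimension in 5.5 do.
- **Dosing rules.** Protocol 5.7.2.1 to 5.7.2.3 refer to drug-related events without saying whether 8.1 or 8.9 decides.

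**The case against.** The strongest reply is that this is one loosely drafted clause. Possible, Probable and Definite share the key phrase of Related, and Unlikely shares that of Not related, so an investigator facing a dual-cause event has a category that fits directly and must pass over it to choose Unrelated. The dosing rules also leave room for judgement: 5.7.2.1 allows nivolumab to be delayed for any AE that in the investigator's view warrants it, and 5.7.2.3 requires discontinuation for any AE judged a substantial clinical risk. Finally, the electronic CRF and the SAE pages are not among the documents and may already resolve the choice.

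Much of this stands, and it rules out several stronger readings that a reader might infer.

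- *The two scales are incompatible throughout.* They are not: four of the five categories in 8.9 map onto 8.1.
- *Drug reactions drop out of SUSAR assessment.* For SAE inside the window, 8.2 and 8.10.1 do not support this.
- *Drug reactions disappear from related-event tables.* The SAP plans no table restricted to related events.
- *The length of AE follow-up depends on attribution.* Flow chart notes 6 and 14 speak of drug-related events, but Protocol 7.7.3.1, 8.1.1 and 8.2 set follow-up by grade, resolution or stabilization, regardless of relatedness.

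The contradiction itself is not answered. A stated rule, not a mere silence, permits an event that is Related under 8.1 to be recorded as Unrelated. Unseen forms might mitigate that, but the protocol text would still disagree with itself.

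**Conclusion.** Wrong as written: an internal inconsistency of minor severity. It is confined to the second limb of Unrelated in 8.9, and to events with both a reasonable drug cause and a reasonable other cause. For those events the text allows either Unrelated or Possible, while 8.1 allows only Related.

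The practical effect falls on late SAE reporting, on causality reporting under SAP 5.2 and 5.5, on non-serious AE, and on the unnamed scale behind the drug-related dosing rules. The primary end point and the all-cause safety comparisons are untouched. I give no count of affected events: the documents contain neither adverse event rates nor the share with a competing cause, and an invented figure would add nothing. The conclusion rests on the literal wording of 8.1 and 8.9 and on no precedence rule appearing elsewhere in the two documents. Investigators may in practice choose Possible, in which case the effect would be small.

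**What to change.** 1. In Protocol 8.9 and the CRF, limit the alternative-cause limb of Unrelated to events that have no reasonable causal relationship to an IMP.
2. State in the protocol and the SAP that Possible, Probable and Definite correspond to Related, and Unrelated and Unlikely to Not related, for late-SAE reporting, SUSAR evaluation and SAP causality reporting.
3. For the drug-related delay, resumption and discontinuation rules in Protocol 5.7.2.1 to 5.7.2.3, the sponsor should reconcile the passages and state which scale governs. Which attribution level should trigger a dosing action is a clinical decision and is not proposed here.

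The cost is a rewording of the protocol and CRF and one sentence in the SAP. The downside is that slightly more events will be counted as related. The change is best made before events are recorded: an entry of Unrelated does not show which limb was used, so entries already made would have to be reviewed individually.
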